**Table 7: Clinical Endpoints**

Outcome	Included Patients	Point of Measurement	Definition
Feasibility	All	Interim Analysis/Safety Follow-Up Visit (see Section 6.5.1)	Descriptive summary of all adverse events (number, severity and duration of adverse events) according to NCI-Common Terminology Criteria for Adverse Events (CTCAE) v4.0
Efficacy	All	Following cycles 2, 4, 6, 8 and at progression/off-study time-point	Descriptive summary of conventional response criteria as described in Appendix A. In addition any clinical information regarding MRD status (eg: flow cytometry, cytogenetics, PCR) will be captured at these time-points.
Time to first response	Responders (mCR, mCRi,, CR, CRi, PR)	As above	Defined as time from start of study to initial achievement of first response.
Time to best response	As above	As above	Defined as time from start of study to initial achievement of best response.
Duration of response	As above	As above	Defined as time from initial achievement of response to loss of response.
Duration of best response	As above	As above	Defined as time from initial achievement of best response to loss of best response.
Overall survival	All	Entry onto trial	Death from any cause

**Bone marrow examinations for clinical response assessment will be performed pre-treatment and after cycles 2, 4, 6 and 8 (or the progression/off-study time-point).** Bone marrows after cycles 2, 4, 6 and 8 may be performed anytime in the week prior to the next cycle of Pembrolizumab (*ie:* the “after cycle 2” marrow may be performed prior to the pembrolizumab dose on day 1 of cycle 3 or anytime in the preceding week). Assessments will include clinical pathological assessment by morphology, flow cytometry and cytogenetics. An additional bone marrow for research purposes may be performed on or around day 8 of cycle 1. Additional bone marrows may be done after cycle 8, until progression as clinically indicated.

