### Response Definitions for AML:

1. **Measurable residual disease (MRD) negative complete remission.** No evidence of residual disease-after clinical assessment by flow cytometry (plus any other technique used in initial diagnosis of residual disease, if applicable). < 5% bone marrow blasts, no Auer rods, no evidence of extramedullary disease. This may be with (**mCR**) or without count recovery to ANC  $\geq$  1,000/mcl and platelet count  $\geq$  100,000/mcl (**mCRi**).
2. **Morphologic complete remission (CR):** ANC  $\geq$  1,000/mcl, platelet count  $\geq$  100,000/mcl, < 5% bone marrow blasts, no Auer rods, no evidence of extramedullary disease. (No requirements for marrow cellularity, hemoglobin concentration).
3. **Morphologic complete remission with incomplete blood count recovery (CRi):** Same as CR but ANC may be < 1,000/mcl and/or platelet count < 100,000/mcl.  
\*Patients with both an ANC < 1000/mcl and platelet count < 100,000/ mcl with at least a 10% marrow cellularity will be reported as a Morphological Leukemia Free State (MLFS).
4. **Partial remission (PR):** ANC  $\geq$  1,000/mcl, platelet count > 100,000/mcl, and at least a 50% decrease in the percentage of marrow aspirate blasts to 5-25%, or marrow blasts < 5% with persistent Auer rods.
5. **Stable disease (SD):** The absence of a complete or partial response, and no progressive disease.
6. **Progressive disease (PD):** Defined as ONE of the following:
  - Greater than 50% relative increase in blasts in the peripheral blood or bone marrow from best assessment with minimum threshold of 20% blasts in the marrow or  $1.0 \times 10^9/L$  blasts in peripheral blood.
  - Development of biopsy proven extramedullary leukemia (if the subject has extramedullary disease at baseline, then PD will be defined by blood and marrow criteria or if new sites of extramedullary disease appear).
  - If subject who present with an initial marrow blast percentage sufficiently high to preclude the ability to base disease progression on a >50% increase in marrow blast percentage, disease progression should be based on peripheral blood criteria or development of extramedullary leukemia as above.
7. **Not Evaluable:** Data incomplete or inadequate for time-point or overall assessment.

Note: Patients entering this study already in morphologic complete remission (ie: CR or CRi) but with evidence of residual disease the only responses possible are mCR, mCRi, SD, PD or NE (see above).

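### Appendix A's only marrow-cellularity threshold runs the wrong way: with residual disease and both counts low, the fuller marrow becomes MLFS and the emptier one stays CRi, a response

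*Combined protocol and SAP*

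**What the plan says.** The rules are in Appendix A, Response Definitions for AML.

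- **Item 2 (CR):** recovered counts, under 5% blasts, no Auer rods, no extramedullary disease. On the marrow itself: "No requirements for marrow cellularity, hemoglobin concentration".
- **Item 3 (CRi):** "Same as CR but ANC may be < 1,000/mcl and/or platelet count < 100,000/mcl". A note adds that patients with both counts low "with at least a 10% marrow cellularity will be reported as a Morphological Leukemia Free State (MLFS".
- **Item 1 (mCR/mCRi):** "No evidence of residual disease-after clinical assessment by flow cytometry", with the same blast, Auer rod and extramedullary conditions, with or without count recovery. No cellularity condition is stated.
- **Item 7 (Not Evaluable):** "Data incomplete or inadequate for time-point or overall assessment".
- **Closing note:** for patients who enter in CR or CRi with residual disease, "the only responses possible are mCR, mCRi, SD, PD or NE".

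Table 7 lists the responders as mCR, mCRi, CR, CRi and PR. It dates time to first response at "initial achievement of first response", with no confirmation. MLFS is not on that list, nor among the responses named in Section 5.9 (continuation) or in the Post-Treatment Active Surveillance section. Section 6.3 says that the marrows after cycles 2, 4, 6 and 8 "may be performed anytime in the week prior to the next cycle of Pembrolizumab".

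**The concern.** A cellularity floor in a remission definition is useful if it keeps a marrow too empty to interpret from being read as cleared. Waiving it for CR is reasonable, because recovered counts show that the marrow is working. When both counts are low, nothing else in the definition shows that, and this is where the note acts on the wrong side of 10%. The marrow with visible recovery gets a separate label. The one that treatment may simply have emptied keeps a label on the responder list, with no flag.

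At stake are the response count, the times to first and best response, and both duration endpoints, all of which use these labels. Section 5.8.2 also treats regrowth after CRi or mCRi as relapse, so an emptied marrow can generate a short response followed by a relapse. Patients who enter in CR or CRi with residual disease are exposed too: without count recovery, mCRi is the only response open to them, and it has no floor. Section 11.3 puts the study in data analysis, so the labels matter now.

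**Working it through.** **1. Labels.** Take under 5% blasts, no Auer rods, no extramedullary disease, ANC below 1,000/mcl and platelets below 100,000/mcl. Items 1 to 3 then give:

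| Residual disease | Cellularity | Label as written | On the Table 7 responder list? |
|---|---|---|---|
| present | 10% or more | MLFS | not listed; status not stated |
| present | below 10% | CRi | yes |
| none | 10% or more | mCRi (MLFS if the note also binds item 1) | yes as mCRi; not stated as MLFS |
| none | below 10% | mCRi | yes |

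No reading of the note removes either row below 10% from CRi or mCRi. Over all 16 combinations of residual disease, ANC, platelets and cellularity, a rule making both-counts-low, below-10% marrows not evaluable changes just those two rows.

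**2. Timing.** Cycles are 21 days, with decitabine on days 8-12 and 15-19 of cycle 1 (Section 5.1). Day 1 of cycle 3 is study day 43, so the after-cycle-2 marrow falls on days 36-43.

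- From the first decitabine dose: 36 − 8 = 28 to 43 − 8 = 35 days.
- From the last dose: 36 − 19 = 17 to 43 − 19 = 24 days. The 3-day dosing allowance in Section 5.3 widens this to 14-27.

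Section 5.2.1 keeps cycle 3 on the same start rule. After that, complete-remission patients without count recovery get five days, given anytime on days 8-19. A course ending on day 12 puts the marrow 36 − 12 = 24 to 43 − 12 = 31 days after the last dose.

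**3. Count recovery.** In the 10-day decitabine series in Section 2.5.2, patients achieving CR passed 100 × 10⁹/L platelets at a median of 39 days (range 31-70) and 10⁹/L granulocytes at 45 days (range 33-70). These match Appendix A's count levels. The clock start is not stated; I assume the start of the course. The marrow at 28-35 days precedes both medians. If the clock ran from the last dose, the comparison would be 17-24 days against the same medians, which is further from recovery.

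**4. Size.** One relabelled patient moves the response rate by 1/10 = 10 points (1/15 = 6.7 points if all 15 permitted subjects were in the denominator). If the next marrow shows remission, first response moves from days 36-43 to days 78-85, which is 42 days later.

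**5. Invented example.** Blasts are 40% at baseline. After cycle 2 they are 2%, with residual disease, cellularity 5% and both counts low. After cycle 4 they are 25%, with low counts.

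- As written: CRi after cycle 2. Then 25% exceeds 1.5 × 2% = 3% and the 20% minimum, so the disease has progressed after a response of about 42 days.
- With the cycle 2 marrow not evaluable and not used as the best assessment: 25% is below 1.5 × 40% = 60%, so there is no progression. It is not PR either, because counts are low and the fall is 15/40 = 37.5%, short of 50%. The result is stable disease and no response.

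**The case against.** **Item 7 could absorb these marrows.** A pathologist may call an empty marrow inadequate. That is possible, but item 7 mentions neither cellularity nor aplasia, and item 2 says cellularity is not required. The argument is stronger for mCRi, since item 1 contains no waiver. It still leaves the matter to case-by-case discretion.

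**Low counts do not prove empty marrows.** This stands. Section 2.5.2 reports blood counts, and the documents give no cellularity after decitabine. Nor does emptying by itself lower the blast percentage, which Appendix A calculates as a share of nucleated marrow cells. Cellularity is also not the only clue: CBC and reticulocytes are taken before each cycle (Section 6.2), and another induction marrow follows six weeks after those at cycles 2, 4 and 6. But the response labels do not use reticulocytes, and Table 7 does not wait for a later marrow.

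**Stronger readings the documents do not support.**

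- *Every both-counts-low marrow is a response.* This needs MLFS to count as CRi, which is nowhere stated.
- *The fuller-versus-emptier contrast applies to mCRi as well.* The note sits under item 3, so the contrast is certain only where residual disease is present.
- *The 17-24 day gap holds throughout.* The five-day dosing in Section 5.2.1 can lengthen it after the cycle 5 and 7 courses.
- *A particular fall in response rate can be forecast.* Section 2.5.2 gives 19% CRi in a decitabine series, but not how many had both counts low or an empty marrow.

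**Conclusion.** The point holds on the text. For a marrow with under 5% blasts, residual disease and both counts low, the 10% threshold separates out the fuller marrow and leaves the emptier one as an unflagged CRi. With no residual disease, a marrow below 10% is mCRi for lack of any floor. This is a written rule that can count an emptied marrow as a response.

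Severity is minor. Only marrows with both counts low and cellularity below 10% are touched. Their number is not in the documents and may be zero. Each would move the rate 10 points at N=10 and could shift first response by 42 days. The endpoints are secondary and descriptive (Sections 2.7 and 8.4), and the safety stopping rule does not use them. That the case is likely to arise rests on the assumed clock start and on the cited series carrying over to this combination.

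A reader might infer that a late correction is harmless because it can only be conservative. That is true of the response count only, and only if MLFS is handled the same way in both versions. Durations are measured in responders alone, so dropping a short response can lengthen the reported duration, and a relapse can become stable disease. Both versions therefore have to be shown.

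**What to change.** **For the analysis under way**

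1. List marrow cellularity for every CRi or mCRi time-point with ANC below 1,000/mcl and platelets below 100,000/mcl.
2. Where it is below 10%, treat the time-point as Not Evaluable and use the next scheduled marrow, with no extra biopsy. If there is no later marrow, the time-point stays Not Evaluable. Describe this as an added rule, since item 7 does not itself say so.
3. Report response count, times and durations by the written rule and by this one, side by side.
4. Put MLFS on its own line, state whether it counts as a response, and apply that choice in both versions.

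**For any reuse of Appendix A**, add to items 1 and 3: if both counts are low, marrow cellularity must be at least 10%; otherwise the time-point is not evaluable and the next scheduled marrow is used.

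**Cost:** a look-up in marrow reports on file for the few patients concerned, a second run of the response summaries, and one sentence in Appendix A.

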### 5.8.2. Off-Study Criteria

A subject must be removed *from the study* for any of the following reasons:

- Confirmed disease progression despite at least two cycles of hypomethylating agent therapy and/or four doses of pembrolizumab. For these purposes disease progression is defined as greater than 50% relative increase in blasts in the peripheral blood or bone marrow or development of extramedullary disease (see Appendix A) at a therapy response assessment time-point (see Appendix G) compared to before start of treatment or relapse in those previously in complete remission (mCR/mCRi, CR/CRi).
- Patient meets off-treatment criteria but is not eligible, or declines, active surveillance phase
- The subject has a confirmed positive serum pregnancy test
- Subject becomes significantly noncompliant with study drug administration, study procedures, or study requirements, which might increase risk or substantially compromise the interpretation of study results.
- The subject is lost to follow-up
- The subject completes two years on study
- Administrative reasons
- The subject or legal representative (such as a parent or legal guardian) withdraws consent
- Investigator's decision to withdraw the subject from the study

The end of treatment and follow-up visit procedures are listed in Section 6.

The End of Treatment and Follow-up visit procedures are listed in Section 6. After the end of treatment, each subject will be followed for 30 days for adverse event monitoring. Subjects who discontinue for reasons other than progressive disease will have post-treatment follow-up for disease status until disease progression, initiating another cancer treatment, withdrawing consent or becoming lost to follow-up. After study withdrawal each subject will be offered the opportunity to consent to an alternative hematology branch protocol (eg: 94-H-0010) to allow follow-up by telephone at approximately three monthly intervals for overall survival until death, withdrawal of consent, or the closing of the study protocol, whichever occurs first.

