## **6.0 CLINICAL MONITORING**

### **6.1. Study Evaluations: Screening/Baseline**

**Screening:** Screening period will consist of the 28 days prior to C1 starting. During this time, patients will complete the necessary screening studies and testing. These will ordinarily be performed, prior to a patient signing consent for this protocol, on another screening Hematology Branch protocol (eg: 97-H-0041).

- Complete medical history
- ECOG performance evaluation

17-H-0026 (PD-AML)

[name], BM BCh DPhil

September 27, 2019

- Physical exam
  - Concomitant medication review
  - Complete blood count (CBC) with differential
  - Acute care & mineral panels (includes Na, K, Cl, CO2, creatinine, glucose, BUN, phosphorus, magnesium, albumin, and calcium)
  - Total protein, CK, Uric Acid, and LDH
  - Hepatic panel (includes alkaline phosphatase, ALT, AST, total bilirubin, and direct bilirubin)
  - Reticulocyte count
  - PT, PTT, fibrinogen
  - Thyroid function tests
  - Type and screen
  - Urinalysis
  - HLA typing
  - EKG
  - G6PD testing (as clinically indicated)
  - CMV IgG, IgM and PCR
  - Viral studies (serologies for HIV 1/2, hepatitis B and C). For individuals with a positive hepatitis B core antibody, HBV DNA PCR will be performed.
  - Peripheral blood flow cytometry (AML and T/B/NK).
- For females of childbearing potential, one negative pregnancy tests sensitive to 50 mIU within 72 hours prior to starting study drug.
- Baseline non-contrast computerized tomography scans of chest and sinus will be performed prior to, or in first five days after treatment initiation. Further baseline imaging will not be routinely performed except for those with a history of extra-medullary myeloid disease (also known as granulocytic sarcoma, myeloid sarcoma, or chloroma), another malignancy or disease where imaging represents the clinical standard of care, or suspicion for extra-medullary myeloid disease or ongoing infection.
- Baseline bone marrow aspiration and biopsy
    - Morphology and immunohistochemistry
    - Cytogenetics (karyotype) and/or FISH.
    - AML molecular testing panel (e.g.: c-Kit, FLT3-ITD, NPM1 or CEBPA mutation)
    - Flow cytometry

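### In Appendix A, with a persisting extramedullary site and recovered counts, marrow blasts cut to 5-25% score PR, but marrow cleared below 5% without Auer rods scores only stable disease

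*Combined protocol and SAP*

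**What the plan says.** The response categories are in Appendix A, Response Definitions for AML.

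- **Complete remission (items 1-3).** CR requires "< 5% bone marrow blasts, no Auer rods, no evidence of extramedullary disease", plus recovered counts. The MRD-negative categories mCR and mCRi carry the same marrow and extramedullary conditions. CRi is "Same as CR but ANC may be < 1,000/mcl and/or platelet count < 100,000/mcl", so it inherits the extramedullary condition and relaxes only the counts.
- **PR (item 4).** ANC of at least 1,000/mcl, platelets above 100,000/mcl, and "at least a 50% decrease in the percentage of marrow aspirate blasts to 5-25%, or marrow blasts < 5% with persistent Auer rods". Extramedullary disease is not mentioned.
- **SD (item 5).** "The absence of a complete or partial response, and no progressive disease". This is the remainder category.

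Patients with extramedullary disease can enter. Section 4.2 excludes only known CNS involvement. Section 6.1 limits further baseline imaging "except for those with a history of extra-medullary myeloid disease" and a few other situations. Item 6 of Appendix A has a clause for them: "if the subject has extramedullary disease at baseline, then PD will be defined by blood and marrow criteria".

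Table 7 counts mCR, mCRi, CR, CRi and PR as responders and leaves SD out. The Post-Treatment Active Surveillance Phase in section 6.5 is open to patients in complete or partial remission, and again not to SD.

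**The concern.** A response scale should not fall as the disease measure improves. Here it does, for one type of patient. If the extramedullary site persists, the complete remission categories are closed. PR then accepts marrow blasts from 5% to 25%, but accepts blasts below 5% only if Auer rods persist. A marrow that clears fully, Auer rods included, fits neither and drops to SD.

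Time to first response, time to best response and the two duration endpoints in Table 7 all depend on this label. A patient first assessed with a cleared marrow would be a non-responder. A patient who was PR and then cleared the marrow would move to SD, and could be recorded as having lost the response by improving. The label also decides whether such a patient qualifies for active surveillance.

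**Working it through.** This is a check of classification logic. The plan gives no figure to reproduce.

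**Inputs.** Items 1-6 of Appendix A, applied literally. Assumed example: baseline marrow blasts 40%, ANC 1,500/mcl, platelets 150,000/mcl, no new extramedullary site and no circulating blasts.

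**Limits for this baseline.** A fall of at least 50% means blasts of at most 0.5 × 40% = 20%, so the first limb of PR covers 5% to 20%. Marrow progression needs more than 1.5 × 40% = 60%.

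| Marrow blasts at assessment | Site cleared, no Auer rods | Site persists, no Auer rods | Site persists, Auer rods persist |
|---|---|---|---|
| 2% or 4.9% | CR | **SD** | PR |
| 5%, 15% or 20% | PR | **PR** | PR |
| 30%, 40% or 59% | SD | SD | SD |
| 61% | PD | PD | PD |

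(CR in the first row assumes that residual disease is still detectable; otherwise it is mCR.)

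**Reading the table.**

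1. In the first response column the order is right: CR, PR, SD, PD. The inversion arises only when the site persists.
2. In the middle column, 40% to 15% is PR and 40% to 2% is SD.
3. In the first row with the site persisting, a marrow that keeps its Auer rods is PR, and one that has lost them is SD. This is the same inversion in another form.

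**Where it does not arise.** With ANC 500/mcl, and with ANC 500/mcl and platelets 50,000/mcl together, every marrow value from 2% to 59% is SD while the site persists. PR fails on counts and CRi fails on the site. The same follows from item 4 if only platelets are low. The first limb of PR also needs a baseline of at least 10%, because half of anything lower is below 5%.

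**Possible effect on duration.** Cycles are 21 days. PR after cycle 2 (week 6) and marrow clearance after cycle 4 (week 12) would give a recorded duration of 12 - 6 = 6 weeks, if a move from PR to SD is taken as loss of response. Table 7 does not define loss of response, so this is one possible reading.

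**Size of one patient.** 1/10 = 10 percentage points at the planned size, or 1/15 = 6.7 points at the maximum accrual.

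**The case against.** The best case against the point is that it is narrow. It needs baseline extramedullary disease, a site that persists, marrow below 5%, no Auer rods, and both counts recovered. Sections 5.2.1 and 9.1.2 say that severe cytopenias are expected, so recovered counts will not be common. Efficacy is descriptive, and section 2.7 says that the study is not powered for it. With about 10 patients, each course can be described individually. Section 11.3 says that accrual closed in November 2017 and that the study is in data analysis only. All of this stands and limits the weight of the point. None of it repairs the scale, and no other section does so.

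A reader might go further in four ways that the documents do not support.

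- **That ignoring growth of a known site is an error.** Item 6 states the rule openly for these patients: "PD will be defined by blood and marrow criteria or if new sites of extramedullary disease appear". That is a clear choice, even if one would choose otherwise. Appendix G schedules no follow-up imaging from which growth could be judged evenly.
- **That continuation of treatment is affected.** Section 5.9 treats PR and SD alike, so the inversion changes nothing there.
- **That the chance of misclassification is high.** At assumed frequencies of 3%, 10% and 20%, 1 - (1 - p)^10 gives 26%, 65% and 89%. These are chances that at least one of 10 patients has extramedullary disease. The chance of a wrong category is lower, because the other conditions must hold too.
- **That the recorded duration must be six weeks.** This depends on a definition of loss of response that the plan does not give.

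**Conclusion.** The point holds in a limited form. On the literal text, a patient with a persisting extramedullary site, recovered counts and no Auer rods is PR when marrow blasts fall by at least half to 5-25%, and SD when they fall further to below 5%. The deeper marrow response is then left out of the Table 7 responders and out of active surveillance, and may be read as loss of an earlier PR.

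Only descriptive secondary endpoints are touched; the primary feasibility summary is not. The number of patients with baseline extramedullary disease is not in the documents and may be zero. If one patient is affected, the response proportion shifts by 10 percentage points in 10. The conclusion assumes that Appendix A is applied as written, without an unwritten convention for these patients.

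**What to change.** In item 4, for response scoring, add a limb for patients whose baseline marrow blasts were at least 5%: *or a fall of at least half, to below 5% marrow blasts without Auer rods, while extramedullary disease persists*, with the same count requirements as the rest of PR. State also that going from 5-25% to below 5% marrow blasts with a persisting site is not loss of response.

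The baseline condition and the required fall are both needed. Without them, a patient with extramedullary disease only, marrow below 5% throughout and good counts would be scored PR with no change at all.

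State that the progression rule for leaving the study in section 5.8.2 is unaffected. Leave item 6 as it is. The sponsor should also say whether the active surveillance criterion follows the revised label or the present one, so that the two sections agree.

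The sponsor can first check whether any enrolled patient had baseline extramedullary disease. If one is affected, report the category under the current text and the rescored category side by side, and label the second as post hoc. The cost is one extra classification line and a labelled rescoring for any affected patient. No new procedure is needed, because judging CR already requires deciding whether the site is still present.

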### **5.9. Optional Continuation Phase after Eight Cycles of Pembrolizumab**

As described in section 5.1 this pilot study is intended to offer a total of eight doses of pembrolizumab on every three weekly cycles with decitabine given on alternative cycles as initial induction therapy.

In the event that a patient achieves a response of mCR, mCRi, CR, CRi, PR or SD (see Appendix A) at the end of cycle 8 assessment then additional cycles of pembrolizumab and decitabine therapy will be offered. These additional cycles will be given according to the same schedule (see section 5.1) with the below exceptions. Pembrolizumab in cycle 9 (ie: first cycle of continuation phase) may be delayed up to 7 days to allow post-induction phase staging to be completed. No more than 35 cycles (ie: two years) of therapy will be offered. Decitabine 20 mg/m^2 will be given for not more than ten consecutive days every six weeks and may be prescribed and supplied by non-study physician.

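### Appendix A measures progression from best assessment but sets the marrow criterion aside by the initial blast percentage, so the same marrow relapse can be scored PD or SD

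*Combined protocol and SAP*

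**What the plan says.** Appendix A, Response Definitions for AML, item 6, gives progressive disease (PD) as three bullets under the words "Defined as ONE of the following".

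- Bullet 1: "Greater than 50% relative increase in blasts in the peripheral blood or bone marrow from best assessment", with a floor of 20% blasts in the marrow or 1.0 x 10^9/L in the blood.
- Bullet 2: biopsy-proven extramedullary leukemia.
- Bullet 3: where a subject has "an initial marrow blast percentage sufficiently high to preclude the ability to base disease progression on a >50% increase in marrow blast percentage", then "disease progression should be based on peripheral blood criteria or development of extramedullary leukemia as above". It gives no numerical cut-off and no exception for a patient whose blasts later fall.

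Item 5 makes stable disease (SD) the category for a patient with neither a response nor PD. Item 4 requires, for partial remission (PR), recovered counts and "at least a 50% decrease in the percentage of marrow aspirate blasts to 5-25" percent, or fewer than 5% with persistent Auer rods.

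Section 5.8.2 has its own definition of progression for removal from study. It looks for a rise of more than 50% in blood or marrow blasts "compared to before start of treatment", or extramedullary disease. It also counts a relapse after mCR, mCRi, CR or CRi; PR is not in that list.

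Table 7 (Section 6.3) makes the Appendix A categories the efficacy outcome after cycles 2, 4, 6 and 8 and at progression or off-study.

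**The concern.** Bullet 3 exists because a high starting percentage can leave no room for a 50% relative rise. Whether there is room depends on the value from which the rise is measured. In bullet 1 that is the best assessment; in bullet 3 the trigger is the initial value. The two agree for a patient who never improves. They part for a patient who enters very high, improves, and then relapses in the marrow: the marrow criterion can be evaluated again, yet bullet 3 as worded still sets it aside.

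What is at stake is the category reported at that assessment. Under a literal bullet 3 a marrow relapse can be listed as SD, an error that always runs towards better disease control. SD is also one of the categories that counted at the end of cycle 8 under Section 5.9 ("In the event that a patient achieves a response of mCR, mCRi, CR, CRi, PR or SD"), and progression is one of the events that ends the active surveillance phase in Section 6.5.1, which includes PR patients.

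**Working it through.** The plan states no figure to reproduce; the check is arithmetic on its own thresholds.

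**When is a >50% rise impossible?** From a comparator c, PD needs a marrow value above 1.5 x c. This cannot occur when 1.5 x c reaches 100%, so c must be 100/1.5 = 66.7% or more.

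**Bullet 1 threshold.** From best assessment b, the marrow must exceed 1.5 x b and reach at least 20%. In short, the threshold is max(1.5 x b, 20%):

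- after a complete remission of any kind (b below 5%): 20%;
- after PR with b from 5% to 25%: from max(7.5, 20) = 20% to 1.5 x 25 = 37.5%.

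The marrow criterion can therefore be evaluated for every responder, whatever the entry value.

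**Illustrative patients.** In each, blood blasts stay below 1.0 x 10^9/L and not more than 50% above the pre-treatment value, and there is no extramedullary disease. The minimum prior treatment in Section 5.8.2 is taken as met.

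| Marrow blasts: initial, best, current | Bullet 1 | Bullet 3, read literally | Section 5.8.2 |
|---|---|---|---|
| 80%, 15% (PR), 80% | PD: threshold 22.5%; rise (80 - 15)/15 = 433% | not PD | not progression: needs more than 1.5 x 80 = 120%; PR not in the relapse clause |
| 80%, 30% (no formal response), 80% | PD: threshold 45% | not PD | not progression, for the same reasons |
| 80%, 3% (complete remission), 80% | PD: threshold 20% | not PD | progression, through the relapse clause |
| 80%, 80%, 95% (never improved) | cannot be met: needs more than 120% | not PD | not progression |

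In the first row the patient is no longer in PR and, under a literal bullet 3, is not PD, so item 5 gives SD. A patient who reaches 15% without count recovery is in the position of the second row, because PR requires recovered counts. The last row is the only one in which bullet 3 is needed.

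**After tying bullet 3 to the best assessment.** It would apply only when b is about 66.7% or more. The first three rows become PD in Appendix A, and the last keeps its exception. If the pre-treatment marrow counts as an assessment, b is never above the initial value, so no patient who has the marrow criterion today would lose it.

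**How many patients.** The documents give no distribution of entry blasts. If 10% to 30% of patients entered at 66.7% or more (an assumption), that is 1 to 3 of 10. This is a ceiling on those exposed to bullet 3, not a count of misclassified patients: each must also improve and then have a marrow-only rise at an assessment. It may be too high a ceiling, since Section 4.1 also admits patients with residual disease only. Each patient scored differently is 1 of 10, or 10 percentage points, moved between SD and PD at that assessment.

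**The case against.** The strongest reply is that item 6 needs only one bullet to be met, so bullet 1 suffices and the 80%, 15%, 80% patient is PD. Bullet 3 speaks of a percentage that makes a >50% rise unusable, and from a best value of 15% nothing is unusable. That reading is reasonable, and it means the text is ambiguous rather than a certain exclusion. It does not remove the conflict. Blood and extramedullary criteria already stand in bullets 1 and 2, so bullet 3 has an effect only if it restricts bullet 1, and its trigger is the initial value. Two careful assessors could score the same marrow differently.

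A reader might infer that a full marrow relapse in these patients is not progression anywhere in the protocol. The documents do not support that: Section 5.8.2 counts relapse after mCR, mCRi, CR or CRi. For those patients the problem is confined to Appendix A scoring and its disagreement with Section 5.8.2. The gap in both places is limited to patients who reached PR or improved without a formal response.

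A reader might also infer that response durations are inflated. They are not: Table 7 ends them at loss of response, not at PD. A best response already achieved also stands, and Table 7 defines no disease-control proportion.

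Finally, Section 11.3 records accrual closed on November 30, 2017 and the study in data analysis only from March 15, 2019. Consequences during treatment are therefore largely past. What remains is the scoring used in the reports planned in Section 9.8.

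**Conclusion.** The point holds as an internal inconsistency with a small, descriptive effect. Item 6 uses best assessment in bullet 1 and the initial value in bullet 3. For a patient who enters at about 66.7% or more, improves below that, and then has a marrow-only rise of more than 50% from best to at least 20%, the bullets can give PD and SD for the same marrow. After PR, or improvement without a formal response, the baseline comparison in Section 5.8.2 does not capture the event either.

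Only the response category at each assessment is affected. The primary feasibility endpoint (adverse events), the stopping rule, the sample size, best response already achieved and the durations of response are unchanged. The number of patients concerned cannot be derived from the documents.

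The conclusion rests on a literal reading of bullet 3, on the 66.7% cut-off, which follows from arithmetic and is not stated in the plan, and on blood and extramedullary criteria not being met independently.

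**What to change.** In bullet 3, replace the reference to the initial marrow blast percentage with the comparator of bullet 1: the marrow criterion is set aside only when the best-assessment marrow blast percentage is about 66.7% or more, so that a relative rise above 50% is arithmetically impossible. State that the pre-treatment marrow counts as an assessment.

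The cost is one phrase in Appendix A and a re-read of existing results for patients who entered in that range. Marrows were already scheduled after cycles 2, 4, 6 and 8, so no new data are needed. A few assessments may move from SD to PD. Because the study is in data analysis, record the change as a dated clarification of response scoring, and report any category that changes.

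This concerns scoring only. Appendix A item 6 and Section 5.8.2 also differ on the reference point and on relapse after PR; the sponsor should reconcile those passages separately.
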